4.3 STRATEGIES FOR RECRUITMENT AND RETENTION

Patients will be recruited from the practice of [name]. [name] has one of the busiest kidney stone practices in the area providing ample patients to recruit into the study. We do not anticipate any issues with retention as patient involvement will occur at two visits. The first 2 of 3 total urine samples will be collected on the day of the surgical intervention. The 3rd and final urine sample will be collected at an obligatory outpatient follow up visit. The follow up visit is considered obligatory as patients will have their ureteral stents removed at this visit, at which time urine samples may be collected.

5 STUDY INTERVENTION(S) OR EXPERIMENTAL MANIPULATION(S)

5.1 STUDY INTERVENTION(S) OR EXPERIMENTAL MANIPULATION(S) ADMINISTRATION

5.1.1 STUDY INTERVENTION OR EXPERIMENTAL MANIPULATION DESCRIPTION

For subjects receiving URS, randomization will occur preoperatively. These subjects will be randomized to undergo lithotripsy with either Ho:YAG or TFL lasers (100 subjects in each arm).

All subjects will undergo surgical interventions that abide by broadly accepted guidelines and standards of care, allowing for slight variations in technique as seen necessary by the attending surgeon [name].

The type of laser that is chosen in SOC is based on hospital availability. That is, most hospitals only have one laser type to choose from (and that laser type is generally contingent on the biomedical contracts the hospital holds with the various laser manufacturers). We are uniquely situated at Mount Sinai West in that we have multiple laser systems to choose from. Multiple surgeons share the lasers, and typically [name] will use whichever laser is already in the room or readily available. Approximately 50% of ureteroscopies were performed with each laser, +/- 10%.

5.2 FIDELITY

5.2.1 INTERVENTIONIST TRAINING AND TRACKING

[name], professor of urology at Mount Sinai West Hospital will be performing the procedures. [name] is a world-renowned expert in these operative techniques.

5.3 MEASURES TO MINIMIZE BIAS: RANDOMIZATION AND BLINDING

Patients will be randomized to receive either Thulium or Holmium laser lithotripsy. Patients will be blinded as they will be anesthetized during the operation. Blinding of the operators would not be possible owing to the differences in laser modalities.

We will utilize random.org which is a validated tool that utilizes atmospheric noise to generate random numbers. Each enrolled patient will be given a subject ID (1-108, consecutively assigned) and these study IDs will be entered as string of integers to random.org and randomized prior to the initiation of the study.

This process will determine group assignments. This will ensure both true randomization and equal allocation... The laser systems are bulky and require transfer into and out of the operating room preoperatively as the OR staff prepares for the upcoming case. Thus, though it only takes a few minutes to actually switch the laser systems, we tend to use the laser that is already in the operating room. The purpose of randomization is to remove this 'last case' bias and ensure equal distribution of laser the modality used.

6 STUDY INTERVENTION/EXPERIMENTAL MANIPULATION DISCONTINUATION AND PARTICIPANT DISCONTINUATION/WITHDRAWAL

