1.2 SCHEMA

Patient eligibility will be confirmed during initial presentation of kidney stone, wherein [name] will determine if the patient is eligible to participate based on their clinical characteristics. [name] will determine if URS will be performed based upon available imaging studies and urologic standard of care. If so, [name] will explain the specifics of the study to the patient and ask if he or she is willing to participate. All patients will have pre- and postoperative urine samples collected which will be stored and analyzed for protein biomarkers at a later date.

A member of the research team will approach the patient after [name] has introduced the study and the patient agrees to learn more. Once informed consent has been achieved, patients will be randomly placed into one of two groups that will indicate which type of laser lithotripsy they will receive:

- 1) Hol:YAG laser
- 2) Thulium laser

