9.1.2 CONFIDENTIALITY AND PRIVACY

The data will be housed in Mount Sinai's REDCap database. The data is anonymous, and no identifiers are collected. The data will be stored with protected passwords. The data will be reported to the sites in aggregate and anonymized. The publication will also not mention any center by name. The results in the publication will be in aggregate form and anonymous.

Urine and blood samples will be kept in a secure freezer in the Mount Sinai West pathology lab, and then will be transported to our main lab at the Icahn School of medicine for analysis. Only study staff will have access to these samples.

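### Section 5.3 fixes the laser for every subject ID before the study and assigns IDs in order, but nothing conceals the list from the unblinded surgeon or recruiting staff

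*Combined protocol and SAP*

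**What the plan says.** Section 5.3 describes the mechanism in three steps. On numbering: "Each enrolled patient will be given a subject ID (1-108, consecutively assigned". On timing: "these study IDs will be entered as string of integers to random.org and randomized prior to the initiation of the study". On effect: "This process will determine group assignments", with the added assurance "This will ensure both true randomization and equal allocation". The same section states "Blinding of the operators would not be possible owing to the differences in laser modalities". It gives the purpose of randomising as removing a habit: "we tend to use the laser that is already in the operating room".

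On who does what, section 1.2 has a clinician (name removed) who "will determine if the patient is eligible to participate based on their clinical characteristics". That clinician also decides whether ureteroscopy is done and introduces the study, after which a research team member approaches the patient. Section 1.2 places group assignment after informed consent, and section 6.2 treats a patient as enrolled at signature. Section 9.1.1.1 allows signature at the office visit or, for patients who want more time, on the day of surgery.

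Section 9.1.2 mentions a "REDCap database", but only as the place where data are kept.

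**The concern.** Two things protect a randomised comparison at entry: an unpredictable sequence, and concealment of that sequence from those who decide who enters and when. Section 5.3 deals with the first and is silent on the second. With consecutive IDs the next ID is always the last one plus one, so a person who can see the list can read off the next laser.

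If that person also judges eligibility, or decides whom to approach and when, the choice or order of patients can come to depend on the laser. The arms could then differ at entry, and the preference that randomisation was meant to remove could return through enrolment. The preoperative urine sample and the regression in section 8.4.2 could correct part of such an imbalance where it is measured, but not where it is unmeasured.

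**Working it through.** **List length.** Section 8.2 gives 98 patients and 10% dropout: 98 × 1.10 = 107.8, rounded up to 108. This matches the 108 IDs in section 5.3. (Dividing instead, 98 / 0.90 = 108.9, gives 109; nothing here depends on the difference.) Section 5.1.1 states 100 subjects in each arm, which fits neither figure and needs reconciling before a list is built. I use 108.

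**Is there a concealment step?** Going through the relevant sections:

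| Question | Where the plan speaks | Answer |
|---|---|---|
| When is the sequence made? | 5.3 | Before the study starts |
| How is a patient linked to it? | 5.3 | Next consecutive ID |
| When is the patient assigned? | 1.2, 6.2 | After consent |
| Who generates or holds the list? | Nowhere | Not stated |
| Who is kept from seeing it? | Nowhere | Not stated |
| What releases an assignment? | Nowhere | No envelopes, independent holder or locked system described |

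**Is the surgeon also the gatekeeper?** Patients come from one clinician's practice (4.3), must be scheduled for ureteroscopy with a named clinician (4.1), and are operated on by one professor of urology (5.2.1). Eligibility and introduction to the study rest with a named clinician (1.2). The names are removed, so treating these as one person is a strong inference and not a literal statement. If they are different people, the question simply moves to whichever of them, or of the recruiting staff, can see the list.

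**Does assignment after consent settle it?** No. That rule fixes when a patient formally receives a group. It does not hide what the next ID will bring while the earlier decisions are being made: whether the patient is eligible, whether and when to approach, and whether consent is taken now or on the day of surgery.

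**How foreseeable are the assignments?**
- List visible: 108 of 108.
- List hidden, past assignments known. I take equal allocation to mean 54:54 in one unblocked permutation, since the plan describes no blocks. Best guessing names whichever laser has been used less so far. Expected correct guesses = m + (2^(2m) / C(2m, m) − 1) / 2, with m = 54.
- The ratio 2^108 / C(108, 54) is about 13.055, so the result is 54 + (13.055 − 1) / 2 = 54 + 6.03 = 60.03, and 60.03 / 108 = 55.6%. A simulation of 20,000 lists gave 60.04.
- Pure chance: 54 of 108, or 50%.

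Access to the list is therefore what matters. The equal-split restriction adds only about six correct guesses. The proposed change keeps the sequence, so the 60 of 108 would remain; what it removes is the route to 108 of 108.

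**The case against.** A reader might infer that generating the list in advance is the fault, or that the surgeon does see it. The documents support neither. Preparing a sequence beforehand against numbered IDs is ordinary practice, and the fix keeps it. No section says that the surgeon or recruiters have access. The text of section 5.3 has an ellipsis after the equal-allocation sentence, so something may have been lost there. Section 9.1.4 also refers to a manual of procedures that is not among the documents and might contain the step.

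A reader might also infer a strong motive to steer. The only documented one is convenience, namely which machine is already in the room, and it has no stated link to a patient's risk of renal injury. Section 3.2 says surgeons do not usually choose a laser beforehand, section 5.1.1 reports roughly even use, and section 5.3 says switching takes only a few minutes. Consent is normally taken at the office visit, before the machine in the room matters; mainly the day-of-surgery option leaves room for this motive. A research team member, not only the surgeon, approaches the patient.

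All of this stands and lowers the likelihood of harm. None of it conceals the sequence.

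**Conclusion.** The point holds as a gap in the procedure. A pre-assigned list tied to consecutive IDs, with an unblinded operator, has no stated concealment from the surgeon or recruiting staff. It rests on two assumptions: that the clinician who judges eligibility is the operating surgeon (or that recruiters could see the list), and that no concealment step exists in a document not supplied.

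Its size can be given only as foreseeability: all 108 assignments with access to the list, against about 60 without it. A reader might go further and infer a particular shift in a biomarker or a particular false-positive rate. That would need a steered fraction and a difference in injury risk that the documents do not supply, and relating a shift to the 40% limit in section 8.2 would mean guessing what the 40% is a percentage of. I give no such figure. Nor would I say that any resulting bias is wholly beyond repair, since measured imbalance can be partly adjusted.

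I class this as a cheap improvement.

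**What to change.** In section 5.3, replace the open pre-assigned ID list with a concealed one:

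- Name who generates and holds the sequence. This should be an existing team member who takes no part in recruitment or surgery.
- Load the random.org sequence into a locked randomisation module of the REDCap system, if one is available; section 9.1.2 establishes only a database. Otherwise have that team member prepare sequentially numbered, sealed, opaque envelopes.
- Release each assignment only after eligibility is recorded and consent is signed, and log the time of release. Sections 1.2 and 6.2 already place assignment after consent; what is new is that the assignment cannot be known before then. Holding release until the day of surgery is optional.
- If the manual of procedures already contains such a step, cite it in 5.3.

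The cost is a paragraph of protocol text and a small one-time set-up, with no extra patients or visits. Operating-room staff may learn the laser somewhat later, which the short switching time stated in section 5.3 suggests is workable.

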6.1 DISCONTINUATION OF STUDY INTERVENTION/EXPERIMENTAL MANIPULATION

No discontinuation will take place as the surgical procedures being performed are part of subjects' standard clinical care.

6.2 PARTICIPANT DISCONTINUATION/WITHDRAWAL FROM THE STUDY

Patients will be considered enrolled in the study once consent has been signed. Participants may discontinue or withdraw from the study for any reason and at any point in time through the conclusion of the study. If a participant desires withdrawal after some or all of their urine samples have been collected or analyzed, their urine samples will be discarded in a biohazard-safe and anonymous fashion.

6.3 LOST TO FOLLOW-UP

A single follow up visit is required to complete enrollment criteria for this study. Participants who fail to show up to their first follow up appointment for stent removal will be automatically withdrawn from the study and previously collected urine samples will be discarded as above.

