4.2 EXCLUSION CRITERIA

-Exclusion Criteria:

- Multiple or bilateral renal/ureteral stones
- Staghorn calculi
- History of chronic kidney disease or ESRD
- Presence of indwelling ureteral stent or nephrostomy tube at time of recruitment
- Urinary tract infection (cystitis or pyelonephritis) within 2 weeks of recruitment
- Development of postoperative septic shock (defined as persistent need for pressors > 1 hour after end of procedure)
- Documented ureteral/renal pelvis perforation

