8.3 POPULATIONS FOR ANALYSES

All enrolled subjects will be included for analyses.

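### Patients are removed for events after randomisation, and missed-visit samples are discarded, which conflicts with analysing all enrolled subjects and can bias the laser comparison

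*Combined protocol and SAP*

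**What the plan says.** The analysis set is given in one sentence of section 8.3: "All enrolled subjects will be included for analyses". Section 6.2 fixes what enrolled means: "Patients will be considered enrolled in the study once consent has been signed". Allocation comes after consent (section 1.2) and before the operation (section 5.1.1): "For subjects receiving URS, randomization will occur preoperatively".

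Other sections then take patients out for things that become known only later:

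- **Septic shock.** Section 4.2 lists it among the exclusion criteria: "Development of postoperative septic shock (defined as persistent need for pressors > 1 hour after end of procedure").
- **No stent.** Section 1.3 restricts the study to stented patients so that the last sample is taken at a standard time. Section 8.2 names unstented patients among the exclusions the enrolment target is meant to cover.
- **Missed visit.** Under section 6.3, a patient who misses the first stent-removal appointment "will be automatically withdrawn from the study and previously collected urine samples will be discarded as above".
- **Perforation.** Section 4.2 also excludes documented ureteral or renal pelvis perforation, without saying whether this means before or during the operation.

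On sample timing, section 4.3 states: "The first 2 of 3 total urine samples will be collected on the day of the surgical intervention". Section 1.3 puts the second of these one hour after the procedure ends. Separately, section 6.2 covers voluntary withdrawal: "If a participant desires withdrawal after some or all of their urine samples have been collected or analyzed, their urine samples will be discarded".

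**The concern.** Randomisation makes the two laser groups comparable at allocation. If membership of the analysis set depends on what happens afterwards, that protection can be lost. Stent status arises under an operator who, by section 5.3, cannot be blinded. Septic shock, and perforation if it occurs during surgery, could themselves be consequences of the procedure. If they reflect laser injury, removing those patients could hide a difference, which matters because section 8.2 states a non-inferiority aim.

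The discarding rule raises a second issue. The preoperative and one-hour samples do not depend on the day-10 visit. The assays run only after enrolment and collection are sufficient (sections 1.3 and 8.1), so a discarded sample leaves no measurement behind and no later reanalysis can restore it.

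**Working it through.** **1. Do the rules fit together?**

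| Rule | Section | When it is known |
|---|---|---|
| Enrolled at consent | 6.2 | Before allocation |
| Randomised preoperatively | 5.1.1 | Allocation |
| Not stented: not included | 1.3, 8.2 | After allocation (a stent already in place at recruitment is excluded by 4.2) |
| Septic shock: excluded | 4.2 | More than 1 hour after the procedure |
| Missed visit: withdrawn, samples discarded | 6.3 | At the day-10 appointment |
| Perforation: excluded | 4.2 | Timing not stated |
| All enrolled analysed | 8.3 | Conflicts with the three removals known after allocation |

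A patient whose samples were destroyed cannot contribute to a biomarker analysis, so 6.3 and 8.3 cannot both be followed.

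**2. Do the removals follow from their own reasons?** The shock criterion needs pressor support beyond one hour, and the second sample is due at one hour. Both day-of-surgery samples are therefore due before a patient can meet the criterion. The stent rule is justified only by the timing of the last sample, which supports a restriction at day 10 and not at one hour.

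**3. The plan's allowance (section 8.2).** 98 × 1.10 = 107.8, rounded up to 108, so the stated target is reproduced. Losses allowed: 108 − 98 = 10, and 10/108 = 9.3%. The named causes are missed follow-up and no stent; the later 10% dropout figure is not tied to a cause. Samples discarded under 6.3 are 2 per missed-visit patient, so 0 to 20 if 0 to 10 of the losses are missed visits.

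**4. Illustration of bias.** The documents give no event rates, so this shows scale only. Assumptions:

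- 108/2 = 54 patients per arm and 10 losses in total;
- SD 2.21 ng/mL, from the ureteroscopy group quoted in section 8.2 (10 patients, two hours after the operation);
- lost patients' mean differs from that of retained patients by d SDs, by the same amount and in the same direction in both arms.

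Each arm's mean moves by (losses/54) × d × 2.21, so the between-arm difference moves by

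shift = (excess losses in one arm / 54) × d × 2.21.

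| Loss split | d = 0.5 | d = 1 | d = 2 |
|---|---|---|---|
| 5/5 | 0 | 0 | 0 |
| 7/3 | 0.08 | 4/54 × 2.21 = 0.16 | 0.33 |
| 10/0 | 0.20 | 10/54 × 2.21 = 0.41 | 0.82 |

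(ng/mL; the sign depends on which arm loses more patients and whether their values are higher or lower.)

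If the 40% limit in section 8.2 applies to its mean of 5.49 ng/mL, the margin is 0.40 × 5.49 = 2.196 ng/mL. The d = 1 shifts are then 0%, 7% (0.164/2.196) and 19% (0.409/2.196) of it. If instead the margin is 1/0.37 = 2.70 ng/mL, they are 0%, 6% and 15%.

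**5. Extreme-case bound on the rank scale.** The planned Kruskal-Wallis test compares ranks, so the matching quantity is the probability that a patient in one arm has a higher value than a patient in the other. Take 54 × 54 = 2,916 pairs, retained patients at 0.50, and lost patients placed at opposite extremes:

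- losses 5/5: (49 × 49 × 0.5 + 5 × 54 + 49 × 5)/2,916 = 0.588;
- losses 10/0: (44 × 54 × 0.5 + 10 × 54)/2,916 = 0.593.

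With the mirror images, the range is 0.41 to 0.59. This is a worst case, not an estimate. It also shows that an even split does not protect the comparison if different kinds of patient are lost in the two arms.

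**The case against.** The best textual defence is that enrolled is used in more than one sense. Section 1.3 calls enrolment complete on receipt of the third sample, and section 6.3 says the follow-up visit is needed to complete the enrolment criteria. Section 8.3 could then mean completers only. But section 6.2 gives an explicit definition, and section 6.3 itself describes these patients as withdrawn. Even if the reading is accepted, the analysis set would still depend on an event after allocation.

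Several other points stand in part:

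- Few visits may be missed. Section 4.3 anticipates no retention problems: "The follow up visit is considered obligatory as patients will have their ureteral stents removed at this visit". Patients are also blinded (section 5.3), so missed visits are less likely to depend on knowing the laser.
- Section 6.3 orders discarding for missed visits only. No section orders it for shock, perforation or no stent.
- The ng/mL figures are weak evidence. The 2.196 ng/mL margin with SD 2.21 gives 32 per arm (one-sided 5%) or 38 (one-sided 2.5%), not the plan's 49, so the 40% may not be a uKIM-1 margin at all. The SD comes from a sampling time this trial does not use, and a mean shift in one marker does not translate directly to rank tests on several.
- Section 8.4.2 names no primary time point. If the primary analysis needs the day-10 sample, keeping the early samples rescues less and the stent restriction is coherent.

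These points limit what can be said about size. They do not remove the contradiction or justify discarding the day-of-surgery samples.

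**Conclusion.** The concern holds. Two facts need no assumption: the analysis set in section 8.3 contradicts the removals in sections 1.3, 4.2 and 6.3, and section 6.3 orders permanent loss of samples that do not depend on the missed visit. Within the planned allowance of 10 losses, that is 0 to 20 samples.

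Bias in the laser comparison is possible but not demonstrated. Its direction and size cannot be determined from the documents, and it is nil if removals are alike in both arms. The shift of 0 to 0.41 ng/mL at d = 1 (0 to 0.82 ng/mL across the values of d shown) rests on assumed loss splits, an assumed difference between lost and retained patients, and a borrowed SD. The 10% allowance protects the number of patients, not the comparability of the arms. This must be fixed because of the contradiction and the irreversible discarding, not because of a shown bias or a loss of power.

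**What to change.** Reconcile sections 1.3, 4.2, 6.2, 6.3 and 8.3 as follows.

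- **8.3:** define the primary analysis set as all randomised patients, analysed by assigned laser with whatever samples they have.
- **6.3:** keep and analyse samples already collected when a visit is missed. Treat only an uncollected third sample as missing; if it comes late, record the actual day.
- **6.2:** discard samples only when a patient asks to withdraw, subject to the consent form.
- **4.2:** do not use postoperative septic shock to remove patients from the primary analysis. State the timing of the perforation criterion; if it includes intraoperative events, treat it the same way.
- **1.3:** apply the stent restriction only to the day-10 analysis or a supporting analysis, not to the one-hour result.
- **Reporting:** give shock, perforation, unstented status, missed visits and voluntary withdrawals by arm, with the analysis excluding these patients as supporting.

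The cost is wording in the protocol and analysis plan, plus a check that the consent form allows samples to be kept after a missed visit. Complicated cases will add some variable values, though the rank test limits their influence. Some third samples will be missing or late, since unstented patients have no guaranteed stent-removal visit. Samples discarded on voluntary withdrawal will still be missing, so section 8.3 should say how those patients are accounted for.
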